Timed Up and Go Test: We will measure the time that the subject takes to rise from a standard arm chair, walk to a tape mark 3-meter away, turn around, walk back to the chair, and sit down [74]. Quantitative, objective metrics of gait function will include stride length and gait speed [75] [80, 81]. We will also use motion analysis system (e.g., motion capture camera, accelerometers/gyroscopes, force platform) to record subject kinematics during the movements.

Knee Proprioceptive Test: Proprioceptive acuity will be assessed by the ability to reproduce self positioning of the leg with eyes closed [74]. The subjects will be seated on a chair, with hips and knees at 90°; the full extension of the leg will represent 180°. The subject's leg will be passively moved and the angle of flexion will be measured at a randomly selected position with a goniometer that will be attached to the subject's leg, this should take approximately 5 seconds. Then the subject's knee will be returned to its original position by the examiner. The subject will then be asked to reproduce the criterion angle and to maintain it for approximately 5 seconds; this angle will also be measured with a goniometer. The difference between the criterion and reproduced angle will be taken as the measure of proprioception acuity. The procedure will be done 3 times. The average of the three procedures will be taken as the proprioceptive acuity for the knee [79].

Knee Extensor/Flexor Force Test: The subject will be seated on a chair with hips and knees flexed to 90 degrees and the maximal voluntary hip flexion and lower leg flexo-extension will be individually measured with a JTech Commander Manual Muscle Testing MMT Device (JTECH medical) on both legs. We will integrate the recorded data with that recorded via the motion

analysis system (e.g., motion capture camera, accelerometers/gyroscopes, force platform) to assess subject kinematics during the movements from the other tests (see above).

Knee Range of Motion (ROM): The knee range of motion (flexion/extension angle) will be measured with a goniometer. [82] The examiner will flex the subject's knee, measuring the maximum knee flexion obtained. The end of the range of knee flexion occurs when resistance is felt and attempt to overcome the resistance cause additional hip flexion. This procedure is validated and standardized as described by Norkin and White [83].

Western Ontario and McMaster Universities Osteoarthritis Index (WOMAC): The WOMAC is a self-reported questionnaire that measures three main components of the impact of OA on quality of life: pain (0-20 score), stiffness (0-8 score) and functional limitation (0-68 score). Physical functioning assessments include a wide range of daily activities, such as bathing and getting in or out of the car.

The Medical Outcomes Study 36-Item Short Form (SF-36): It measures 8-health related concepts using 36 questions and provides a profile of functional health and well-being scores. It also provides a psychometrical index of physical and mental health (note, as stated earlier in this and the subsequent phase of the research the administration of all exams will be completed by a rater blinded to the treatment arm).

VII. BIostatistical Analysis

Data forms and questionnaires will be coded in a standardized manner, and double-entered into our database. Digital measures/recordings will be similarly tracked in our database and regularly backed up. Analyses will be conducted using standard statistical software such as SAS and Matlab. We will use REDCAP as a database (<http://projectredcap.org/>), and personnel entering the data will be blinded.

Sample size calculations and data analysis:

Aim 1: Data forms and questionnaires will be coded in a standardized manner, and double-entered into our database. Digital measures/recordings will be similarly tracked in our database and regularly backed up. Analyses will be conducted using standard statistical software such as SAS and Matlab.

For planning sample size calculation for this study, we utilized the OARSI recommendations for the management of knee OA. In this recommendation [84], a panel of experts reviewed evidence for the most commonly used pharmacological and non-pharmacological interventions for OA pain, giving effect sizes for all these interventions. Examples of non-pharmacological interventions are: education, physical therapy, aerobic exercise, knee brace, footwear, thermal modalities, TENS and acupuncture. Examples of pharmacological treatments are: acetaminophen, NSAIDs, injections with corticosteroids and treatment with glucosamine. In this review, effect sizes vary from 0.06 to 0.72. In fact the largest effect size was shown with injection of corticosteroids. Based on these effect sizes and the effect size we found in our pilot data (1.4), we set the effect size for our sample size calculation considering a effect size smaller or equal than our pilot data and larger than the

larger effect size from this meta-analysis (0.72) [84]. For this particular protocol, we plan a sample size of 64 participants. We considered the same sample per group as four times the subjects in Phase 1: 32 subjects per group. This will be enough to detect a difference in effect size of 0.9 and thus an effect size that is superior than other treatments used in OA according to a large guideline on OA management [84], though we expect a larger effect size for pain. However it is important to be able to detect significance with smaller effect sizes in the Phase 2 work, as some of the neurophysiological outcomes require additional power. Note that the main aim here would still be the comparison of active ESSstim vs. sham ESSstim.

All analyses will be conducted according to the principle of intention-to-treat (using regression-based single imputation method). Intention-to-treat (ITT) population will include all randomized subjects. We will also perform an additional sensitivity analysis in which we will use the method of multiple imputation. The primary outcomes will be pain changes as indexed by VAS scores, biomechanical function changes as indexed with the motion analysis suite (i.e., our biomechanical data acquisition and analysis system), and QOL changes. Differences between the groups will be tested using Student's t-test, and additionally we will adjust for important baseline variables and test the time effect in general mixed longitudinal models. This model will be used for the primary and secondary outcomes (dependent variable (one model for each variable): VAS scores, biomechanical function changes as indexed with the motion analysis suite, and QOL changes, and independent variables will be treatment group and time of assessment (we will also adjust for baseline pain levels in this model)). Secondary analyses will be conducted in an exploratory manner (no correction for multiple comparisons). We will also conduct an EEG analysis to correlate EEG data with pain measures. Similar analysis will be conducted for the adverse effects measuring continuous outcome and for the categorical outcomes we will use Fisher's exact test. In both cases, for safety analysis we will use uncorrected p-value to increase the likelihood of detecting detrimental adverse effects.

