ORGANIZATION OF DETAILED PROTOCOL

Title: Effects of Transcranial Direct Current Stimulation (tDCS) and Transcranial Ultrasound (TUS) on the perception of pain and functional limitations due to Osteoarthritis of the Knee

Protocol 2016P000486

Date: 03/29/2019

I. BACKGROUND AND SIGNIFICANCE

The work to be completed and proposed herein is to be sponsored by the NIH National Center for Complementary and Integrative Health (NCCIH) to evaluate the use of transcranial direct current stimulation (tDCS) applied in conjunction with transcranial ultrasound (TUS) as a treatment for chronic pain due to Osteoarthritis (OA) of the knee. The work we present here is the second part of a 2-Phase plan

Osteoarthritis (OA) of the knee is a leading cause of chronic pain and disability [1]. OA affects 13.9% of adults (aged 25yr +) and 33.6% of the elderly (65yr+), with the knee most commonly

affected [1]. It is estimated that the total cost of OA is up to 2.5% of the US GDP [2], and the burden of OA has only been growing (due to aging and obesity) [1]. Conventional management of OA knee pain is based on a combination of pharmacological and non-pharmacological therapies including oral non-steroidal anti-inflammatory drugs, intra-articular injections, physical therapy, and opioid analgesics [3, 4]. Although these options can show some benefits, they are often associated with significant adverse effects [5, 6] and/or treatment benefits which decrease over time (due to therapy tolerance, disease progression, and/or

Functional and structural imaging studies support the notion that pain in OA is associated with increased activation of pain-related neural networks and that OA pain is correlated with thalamic gray matter volume decreases that can be reversed with decreased pain and increased function [9-17]. Recent evidence demonstrates the correlation between the experience of pain and brain states and recent studies have demonstrated a specific neural signature associated with chronic pain states, as can be indexed by EEG recording, noninvasive brain stimulation (NIBS) based assessments of cortical excitability, and imaging studies [12, 14, 18-26]. These assessments demonstrate specific subcortical-cortical changes in excitability and plasticity that are becoming useful in the development of novel therapies.

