We hypothesize cumulative noninvasive brain stimulation sessions can induce neuroplasticity in brain circuits affected by OA and revert some of the maladaptive compensatory plasticity of the disease [27, 28]. Invasive and noninvasive brain stimulation methods [6, 7, 12, 14, 15, 18, 29] have been shown to be effective in treating chronic pain in some disease states, where it is thought that treatment induced changes in brain activity revert maladaptive plasticity associated with chronic pain sensation [12, 14, 30].

One candidate tool to modulate brain activity and to assess brain activity is transcranial direct current stimulation (tDCS) [39, 40]. Several well-conducted animal studies on the effects of tDCS have been performed in the 1950s and 60s [41-43]. These studies showed that tDCS is a powerful technique to modulate brain function. tDCS has shown some positive effects on chronic pain, most effectively via stimulation of the primary motor cortex (M1) which can lead to significant offline clinical improvements in OA pain based on long-lasting neuroplastic modifications [44-46] (i.e., stimulation effects can outlast the period of stimulation and lead to significant results from days to months following stimulation). However [47], tDCS often elicits suboptimal responses in magnitude and duration of clinical effect. It has been postulated that the inconsistent, suboptimal clinical effects result from the limited focality, penetration, and targeting control of tDCS, highlighting the need for improved noninvasive techniques for OA treatments [40, 48-51].

By combining tDCS with transcranial ultrasound (TUS) it is hoped that some or all of these limitations can be overcome. Transcranial direct current stimulation (tDCS) and transcranial ultrasound (TUS) (e.g., transcranial Doppler ultrasound (TDUS)) are powerful tools to modulate brain excitability and/or to assess brain anatomy (and hemodynamics). Transcranial Ultrasound (TUS) has been used clinically for over 20 years [52, 53] with long established safety guidelines [54], has been used for assessing anatomy and monitoring cerebral hemodynamics; and has been safely used in conjunction with neuromodulation methods like tDCS and transcranial magnetic stimulation (TMS) [55-57] [58-61]. TUS can aid in brain targeting.

[REDACTED]

[REDACTED]

[REDACTED]

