We will recruit up to 94 subjects for this study, with the intention of randomizing exactly 64 subjects with OA of the knee for this study. Once we randomize 64 subjects, we will stop recruiting subjects. Subjects will need to meet all of the following inclusion criteria and none of the following exclusion criteria:

Inclusion Criteria:

1. Able to provide informed consent to participate in the study.
2. Subjects between 18-85 years old.
3. Diagnosis of chronic osteoarthritis with pain of either knee as self-reported. *Prior to beginning baseline procedures this must be confirmed by medical records or a letter from the subject's physician, or diagnosis by a study staff licensed physician. This document may either be brought in by the subject or retrieved by study staff after the subject signs a medical release form. If the subject is unable to obtain the medical record, a diagnosis by a study staff licensed physician will be accepted. After consent, if the subject fails to provide the necessary documentation, or if it cannot be retrieved by study staff, the subject will be considered a screen fail.*
4. Existing knee pain of at least 3 on a 0-10 VAS scale on average over the past 6 months.
5. Pain of at least 3 on a 0-10 VAS scale on average over the week prior to the first stimulation session.
6. Pain resistant to common analgesics and medications for chronic pain used as initial pain management such as Tylenol, Aspirin, Ibuprofen, Soma, Parafon Forte DCS, Zanaflex, and Codeine.
7. Having the ability to feel pain as self-reported.

Exclusion Criteria:

1. Pregnancy or trying to become pregnant in the next 6 months.
2. History of alcohol or drug abuse within the past 6 months as self-reported.
3. Contraindications to transcranial brain stimulation or TUS, e.g. implanted brain medical devices or implanted brain metallic devices.
4. Unstable medical conditions (e.g. uncontrolled diabetes, uncompensated cardiac issues, heart failure or chronic obstructive pulmonary disease).
5. Epilepsy.
6. Use of carbamazepine within the past 6 months as self-reported.
7. Suffering from severe depression (with a score of >30 in the Beck Depression Inventory).
8. History of unexplained fainting spells as self-reported.

9. Head injury resulting in more than a momentary loss of consciousness.
10. History of neurosurgery as self-reported.

V. SUBJECT ENROLLMENT

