There will be 10 stimulation visits to be completed over 2 consecutive weeks (ideally Monday to Friday of each week). The subject will receive either 20 minutes of active tDCS in conjunction with active TUS, or sham tDCS in conjunction with sham TUS per day for the course of their stimulation visits.

Randomization:

Once eligibility and consent have been approved and completed, after all baseline evaluations and immediately before the first stimulation session, stratified blocked randomization will occur using the randomized list generated by an automatic web-based randomization program (www.randomization.com). A staff member who is not involved in any of the study procedures will be responsible for creating the randomization list and monitoring it during the study. Randomization will be stratified by baseline pain, using the median of Phase I as a cutoff (VAS of 7). Subjects will be randomly assigned to treatment or placebo groups in a 1:1 allocation ratio. We will use permuted blocks of variable sizes (4, 6, and 8) in a random manner to minimize the risk of study staff guessing at the next allocation. Randomization order will be kept in sealed envelopes.

Blinding:

All subjects and investigators will be blinded to the group assignment except for the co-investigators providing stimulation and staff involved in the randomization process (the latter would otherwise not be involved in study procedures). Only the staff involved in the randomization will be authorized to break the blind if there is a clinical need as requested by the PI, clinical care providers, Medical Monitor, or IMC. The patients will remain blinded until they have completed all visits (whether they complete all 16 visits or drop out early), or in the case of an adverse event necessitating un-blinding.

If the subject receives a sham stimulation, he/she may re-enroll into an open label portion of the study, where he/she will receive 10 days of active tDCS/TUS. Un-blinded co-investigators (e.g., who provided stimulation) will coordinate with subjects electing to enter into the open label phase, which will be conducted by the un-blinded study staff. The open-label study will be conducted without informing the blinded assessors of the patient enrollment. In the open label phase, we will complete the VAS assessments on Day 5 and Day 10 of stimulation. This collected data will not be analyzed with the main data collected in the study. This data will be used for exploratory analyses only.

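### The exclusion criteria admit Phase 1 participants and others already given tDCS or tDCS/TUS: a small, avoidable risk to the blinding of self-rated outcomes

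*Combined protocol and SAP*

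**What the plan says.** **Eligibility (section IV).** The governing rule is "Subjects will need to meet all of the following inclusion criteria and none of the following exclusion criteria". Ten exclusion criteria follow, numbered without gaps or redaction. Criterion 3 reads "Contraindications to transcranial brain stimulation or TUS, e.g. implanted brain medical devices or implanted brain metallic devices". The last, and the nearest criterion about past procedures on the brain, is "History of neurosurgery as self-reported". None concerns earlier tDCS, TUS or other stimulation, or participation in Phase 1. Two inclusion criteria require average VAS pain of at least 3, over the past 6 months and over the week before the first session. The second is re-checked at Visit 3.

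**Phase 1 (sections I, VI and VII).** The background states "The work we present here is the second part of a 2-Phase plan". The sample size text says "We considered the same sample per group as four times the subjects in Phase 1: 32 subjects per group". Under Randomization, the stratification cutoff of VAS 7 is the Phase 1 median.

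**Duration of effect (section I).** For tDCS of the motor cortex, the background says "stimulation effects can outlast the period of stimulation and lead to significant results from days to months following stimulation".

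**Blinding and outcomes (sections VI and VII).** Sham is tDCS current for less than 30 seconds with the ultrasound transducer off. The protocol states that subjects do not perceive the switching-off and cites a randomized study in support. VAS pain and quality of life are primary outcomes alongside biomechanical function. VAS and WOMAC are described as self-reported. No visit's assessment list includes a question on which arm the subject believes they are in.

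**The concern.** The programme has already recruited people with knee pain for a first phase, and their median pain of 7 lies well above the entry threshold of 3. As the criteria stand, any of them who still meets the pain thresholds may be randomized again, as may anyone treated with tDCS elsewhere. This could matter in two ways, and they are not equally serious.

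- **Recognition.** Blinding depends on the subject not noticing that the sham current has stopped. Someone who has had active stimulation has a reference to compare with. If they identify their arm, their self-rated pain and quality of life can move in opposite directions in the two arms. Randomization does not remove this, because it acts after allocation and by arm. A blinded rater does not protect a score that the subject gives. Without a treatment-guess question it would also go unseen.
- **Carry-over.** If effects last for months, a previously treated subject may start with pain already lowered and have less to gain. Such subjects fall equally into both arms in expectation, so the result is mainly a diluted contrast, not a false one.

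**Working it through.** **1. The plan's own figure.** The plan says 32 per group is enough to detect an effect size of 0.9, without giving alpha, sidedness or power. Assume two-sided 0.05 and n per arm = 2(z_alpha/2 + z_power)² / 0.9². This gives 20, 26 and 33 per arm for 80%, 90% and 95% power. A two-sample t-test with 32 per arm has 94% power at 0.9. The statement is consistent, and the point does not depend on it.

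**2. How many could have felt active stimulation in Phase 1.** If four times is read per group, 32/4 = 8 per Phase 1 group. The number of arms is not given. Assuming two arms, one active, about 8 people had an active course. If four times refers to the whole of Phase 1, there were 8 in all and about 4 active.

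**3. Recognition, in VAS points.** Let k of the 64 be exposed, split evenly between arms, all recognizing their arm, with a spurious between-arm difference of b points among them. The bias in the arm difference is (k/2)/32 × b = k/64 × b. The range b = 1 to 2 points is an assumption; the documents give no figure.

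| k | k/64 | b = 1 | b = 2 |
|---|---|---|---|
| 1 | 0.016 | 0.016 | 0.03 |
| 2 | 0.031 | 0.03 | 0.06 |
| 4 | 0.0625 | 0.06 | 0.125 |
| 8 | 0.125 | 0.125 | 0.25 |

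Each exposed person from outside Phase 1 who recognizes their arm adds a further 1/64 of b. Their number is unknown.

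**4. Recognition, as false-positive rate.** The documents give no VAS standard deviation, so b is now set in SD units. With a two-sided 0.05 t-test and 32 per arm:

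- k = 2, b = 1 SD: bias 0.03 SD, false-positive rate 5.2%.
- k = 8, b = 0.5 SD: bias 0.06 SD, rate 5.7%.
- k = 8, b = 1 SD: bias 0.125 SD, rate 7.8%.

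**5. Carry-over.** In the extreme case where exposed subjects show no further benefit, the effect becomes 0.9 × (1 − k/64).

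- k = 2: 0.87, power 93%.
- k = 4: 0.84, power 91%.
- k = 8: 0.79, power 87%.

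The starting point is 94%. This is loss of power, with no tendency towards a false benefit.

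**The case against.** The strongest case against is that nothing shows that exposed people will enrol. The recruitment sources in section V are referrals, flyers, advertising, registries, medical records, presentations and events; re-contacting earlier participants is not among them. What Phase 1 subjects received is not described in the visible text, nor is the time since Phase 1, nor whether they were told their arm. The protocol cites a randomized study that a 30-second sham blinds reliably, and no passage says that active ultrasound can be felt. Carry-over is limited by the two pain thresholds, the stratification on baseline pain and the model's adjustment for it. The phone questionnaire and medical history are not reproduced and may ask about earlier stimulation.

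Most of this stands, and it limits the size. It does not close the gap. The pain thresholds remove people with little current pain, not people with earlier exposure. A question at screening has no listed criterion to act on. As the protocol describes it, the cited sham evidence concerns tDCS; the text does not say that it covers people who have already felt active stimulation.

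A reader might go further in three ways that the documents do not support:

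- **Counting all of Phase 1.** Two groups of 8 would be 16 of 64 (25%), and 0.25 × 2 = 0.50 points. But recognition needs experience of active stimulation, which under the same two-arm assumption only about 8 had.
- **Inferring that returning responders will enrich the sample, or that carry-over will bias the comparison.** The first has no basis in the text; the second is balanced in expectation by randomization.
- **Treating the open-label option as part of the problem.** Sham subjects who go on to open-label active treatment are kept out of the main analysis.

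**Conclusion.** The gap is real: as written, the criteria admit Phase 1 participants and people already given tDCS or tDCS/TUS to a sham-controlled trial with self-rated primary outcomes. The route that matters is recognition of the arm; carry-over would mainly cost power. The actual size cannot be known from the documents.

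For the Phase 1 pool, 0.125 to 0.25 VAS points is an upper illustration. It rests on a two-arm Phase 1, about 8 active subjects, return and correct recognition by every one of them, and an assumed 1 to 2 point shift. With one or two returners the bias is at most about 0.06 points. The documents do not support a conclusion that the trial will be biased or that its blinding has failed. This is a cheap improvement of low severity.

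**What to change.** Add one exclusion criterion: participation in Phase 1 of this programme, or previous treatment with tDCS or tDCS/TUS. Ask about it at the phone screen.

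If the sponsor does not want to exclude people treated elsewhere, exclude Phase 1 participants, record other prior exposure at screening, and specify a sensitivity analysis without exposed subjects. An end-of-treatment question on believed allocation would also let any recognition be seen.

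The criterion need not extend to TMS: the carry-over passage concerns tDCS, and having had TMS gives no reference for how tDCS/TUS feels.

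The cost is one line, one question and the loss of a few otherwise eligible people. The plan allows up to 94 recruited for 64 randomized, which leaves some room.
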